3.3 Patient Registration

Prior to enrollment on study, patients must be assigned a COG patient ID number. This number is obtained via the COG Registry in the OPEN system once authorization for the release of protected health information (PHI) has been obtained.

3.4 Reservation and Contact Requirements

Before enrolling a patient on study, a reservation must be made through the OPEN website and the Study Chair or Vice Chair should be notified. (The patient will need a COG patient ID number in order to obtain a reservation). Patients must be enrolled within 7 calendar days of making a reservation.

Reservations may be obtained 24-hours a day through the OPEN website.

3.5 Informed Consent/Assent

The investigational nature and objectives of the trial, the procedures and treatments involved and their attendant risks and discomforts, and potential alternative therapies will be carefully explained to the patient or the patient's parents or guardian if the patient is a child, and a signed informed consent and assent will be obtained according to institutional guidelines.

3.6 Screening Procedures

Diagnostic or laboratory studies performed exclusively to determine eligibility for this trial must only be done after obtaining written informed consent. This can be accomplished through one of the following mechanisms: a) the COG screening protocol, b) an IRB-approved institutional screening protocol or c) the study-specific protocol. Documentation of the informed consent for screening will be maintained in the patient's research chart. Studies or procedures that were performed for clinical indications (not exclusively to determine eligibility) may be used for baseline values even if the studies were done before informed consent was obtained.

3.7 Eligibility Checklist

Before the patient can be enrolled, the responsible institutional investigator must sign and date the completed eligibility checklist. A signed copy of the checklist will be uploaded into RAVE immediately following enrollment.

3.8 Institutional Pathology Report

Immediately following enrollment, the institutional pathology report for the diagnosis

THIS PROTOCOL IS FOR RESEARCH PURPOSES ONLY, SEE PAGE 1 FOR USAGE POLICY

under which the patient is being enrolled must be uploaded into RAVE. The report must include the associated study number and COG patient registration and accession numbers. Personal identifiers, including the patient's name and initials must be removed from the institutional pathology report prior to submission.

3.9 Study Enrollment

Patients may be enrolled on the study once all eligibility requirements for the study have been met. Patients who give informed consent for the protocol in order to undergo screening for eligibility are not considered enrolled and should not be enrolled until the screening is completed and they are determined to meet all eligibility criteria. Study enrollment is accomplished by going to the CTSU OPEN (Oncology Patient Enrollment Network) <https://open.ctsu.org/open/>. For questions, please contact the Study Assigned Research Coordinator, or the CTSU OPEN helpdesk at <https://www.ctsu.org/CTSUContact.aspx>. Patients must be enrolled before treatment begins. The date protocol therapy is projected to start must be no later than five (5) calendar days after the date of study enrollment. **Patients must not receive any protocol therapy prior to enrollment.** The only exception to this is for intrathecal cytarabine, which can be given within 1 week prior to administration of flotetuzumab. If IT cytarabine is given prior to enrollment, a separate institutional consent must be obtained.

3.10 Dose Assignment

The dose level will be assigned via OPEN at the time of study enrollment.

4.0 PATIENT ELIGIBILITY

All clinical and laboratory studies to determine eligibility must be performed within 7 days prior to enrollment unless otherwise indicated. Laboratory values used to assess eligibility must be no older than seven (7) days at the start of therapy. Laboratory tests need **not** be repeated if therapy starts **within** seven (7) days of obtaining labs to assess eligibility. If a post-enrollment lab value is outside the limits of eligibility, or laboratory values are older than 7 days, then the following laboratory evaluations must be re-checked within 48 hours prior to initiating therapy: CBC with differential, bilirubin, ALT (SGPT) and serum creatinine. If the recheck is outside the limits of eligibility, the patient may not receive protocol therapy and will be considered off protocol therapy. Imaging studies, bone marrow biopsy and/or aspirate must be obtained within 14 days prior to start of protocol therapy (repeat the tumor imaging if necessary).

Clarification in timing when counting days: As an example, please note that if the patient's last day of prior therapy is September 1st, and the protocol requires waiting at least 7 days for that type of prior therapy, then that patient cannot be enrolled until September 8th.

Important note: The eligibility criteria listed below are interpreted literally and cannot be waived (per COG policy posted 5/11/01). All clinical and laboratory data required for determining eligibility of a patient enrolled on this trial must be available in the patient's medical or research record which will serve as the source document for verification at the time of audit.

4.1 Inclusion Criteria

4.1.1 Age:

Patients must be < 21 years of age at the time of study enrollment.

4.1.2 Weight: Patients must weigh ≥ 17 kg*.

*Weight limit is due to constraints related to the concentration of the current drug formulation. If a new formulation of flotetuzumab becomes available to allow dosing of smaller patients, the protocol will be amended.

4.1.3 Diagnosis: Patients with recurrent or refractory AML are eligible. Patients must have histologic verification of malignancy at relapse.

4.1.4 Disease Status:

- i. Patients with leukemia must have \geq M2 marrow by morphology and/or flow cytometry and one of the following:
 - a. Second or greater relapse
 - b. Refractory after 2 or more chemotherapy cycles
 - c. First relapse after primary chemotherapy-refractory disease
 - d. First relapse after HSCT
- ii. CNS disease:
 - a. Patients must have the status of CNS1 (see [Section 12.3](#)) and no clinical signs or neurologic symptoms suggestive of CNS leukemia, such as cranial palsy.
 - b. Patients with CNS3 or CNS2 status may receive antecedent intrathecal chemotherapy to achieve CNS1 status prior to study entry (see [Section 12.3](#)).
 - c. Patients with a history of CNS chloromatous disease are required to have no radiographic evidence of disease prior to enrollment.

4.1.5 Therapeutic Options: Patient's current disease state must be one for which there is no known curative therapy or therapy proven to prolong survival with an acceptable quality of life.

4.1.6 Performance Level: Patients must have a performance status corresponding to ECOG scores of 0, 1, or 2. Use Karnofsky for patients > 16 years of age and Lansky for patients ≤ 16 years of age (See [Appendix I](#) and https://members.childrensoncologygroup.org/prot/reference_materials.asp under Standard Sections for Protocols). Use appropriate score for study population. **NOTE:** Patients who are unable to walk because of paralysis, but who are up in a wheelchair, will be considered ambulatory for the purpose of assessing the performance score.

4.1.7 Prior Therapy:

4.1.7.1 Patients must have fully recovered from the acute toxic effects of all prior anti-cancer therapy and must meet the following minimum duration from prior anti-cancer directed therapy prior to enrollment. If after the required timeframe, the numerical eligibility criteria are met, e.g., blood count criteria, the patient is considered to have recovered adequately.

- a. Cytotoxic chemotherapy or other anti-cancer agents known to be myelosuppressive. See DVL homepage for commercial and Phase 1 investigational agent classifications. For agents not listed, the duration

THIS PROTOCOL IS FOR RESEARCH PURPOSES ONLY, SEE PAGE 1 FOR USAGE POLICY

of this interval must be discussed with the study chair and the study-assigned Research Coordinator prior to enrollment.

- ≥ 14 days must have elapsed after the completion of other cytotoxic therapy with the exception of hydroxyurea. Additionally, patients must have fully recovered from all acute toxic effects of prior therapy.

NOTE: Cytoreduction with hydroxyurea is recommended to be discontinued ≥ 24 hours prior to the start of protocol therapy.

No waiting period is required for patients having received intrathecal cytarabine, methotrexate, and/or hydrocortisone.

- b. Anti-cancer agents not known to be myelosuppressive (e.g. not associated with reduced platelet or ANC counts): ≥ 7 days after the last dose of agent. See DVL homepage for commercial and Phase 1 investigational agent classifications. For agents not listed, the duration of this interval must be discussed with the study chair and the study-assigned Research Coordinator prior to enrollment.
- c. Antibodies: ≥ 21 days must have elapsed from infusion of last dose of antibody, and toxicity related to prior antibody therapy must be recovered to Grade ≤ 1 .
- d. Corticosteroids: See [Section 4.2.2.1](#). If used to modify immune adverse events related to prior therapy, ≥ 14 days must have elapsed since last dose of corticosteroid.
- e. Hematopoietic growth factors: ≥ 14 days after the last dose of a long-acting growth factor (e.g. pegfilgrastim) or 7 days for short-acting growth factor. For agents that have known adverse events occurring beyond 7 days after administration, this period must be extended beyond the time during which adverse events are known to occur. The duration of this interval must be discussed with the study chair and the study-assigned Research Coordinator.
- f. Interleukins, Interferons and Cytokines (other than Hematopoietic Growth Factors): ≥ 21 days after the completion of interleukins, interferon or cytokines (other than Hematopoietic Growth Factors)
- g. Stem cell Infusions (with or without TBI):
 - Allogeneic (non-autologous) bone marrow or stem cell transplant, or stem cell boost: ≥ 84 days after infusion and no evidence of GVHD.
 - Donor leukocyte infusion: ≥ 42 days.
 - Autologous stem cell infusion including boost infusion: ≥ 42 days.

THIS PROTOCOL IS FOR RESEARCH PURPOSES ONLY, SEE PAGE 1 FOR USAGE POLICY

- h. Cellular Therapy: ≥ 42 days after the completion of any type of cellular therapy (e.g. modified T cells, NK cells, dendritic cells, etc.)
- i. XRT/External Beam Irradiation including Protons: ≥ 14 days after local XRT; ≥ 84 days after TBI, craniospinal XRT or if radiation to $\geq 50\%$ of the pelvis; ≥ 42 days if other substantial BM radiation.
- j. Radiopharmaceutical therapy (e.g., radiolabeled antibody, ^{131}I -MIBG): ≥ 42 days after systemically administered radiopharmaceutical therapy.
- k. Patients must not have received prior exposure to flotetuzumab.

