8.0 EVALUATIONS/MATERIAL AND DATA TO BE ACCESSIONED

8.1 Required Clinical, Laboratory and Disease Evaluation

All clinical and laboratory studies to determine eligibility must be performed within 7 days

THIS PROTOCOL IS FOR RESEARCH PURPOSES ONLY, SEE PAGE 1 FOR USAGE POLICY

prior to enrollment unless otherwise indicated. Laboratory values used to assess eligibility (see [Section 4.0](#)) must be no older than seven (7) days at the start of therapy. Laboratory tests need **not** be repeated if therapy starts **within** seven (7) days of obtaining labs to assess eligibility. If a post-enrollment lab value is outside the limits of eligibility, or laboratory values are older than 7 days, then the following laboratory evaluations must be re-checked within 48 hours prior to initiating therapy: CBC with differential, bilirubin, ALT (SGPT) and serum creatinine. If the recheck is outside the limits of eligibility, the patient may not receive protocol therapy and will be considered off protocol therapy. Imaging studies, bone marrow aspirate, and biopsy must be obtained within 14 days prior to start of protocol therapy (repeat the imaging if necessary).

STUDIES TO BE OBTAINED	Pre-Study	During Cycle 1	Prior to Subsequent Cycles [^]
History	X	Weekly	X
Physical exam with vital signs	X	Weekly	X
Height, weight, BSA	X		X
Performance status	X		
CBC, differential, platelets	X	Twice Weekly (every 3 to 4 days) ³	Weekly ⁴
Pharmacokinetics		X ¹	X ¹
Anti-drug antibody (ADA)		X ¹⁰	X ¹⁰
Urinalysis	X		
Electrolytes including Ca ⁺⁺	X	Twice weekly (every 3 to 4 days) during Week 1, then weekly	X
Creatinine, ALT, bilirubin, AST	X	Weekly	X
Albumin	X		X
Imaging (CT or MRI) of chloroma (if clinically indicated)	X	End of Cycle 1 (if present at baseline)	End of each cycle (if present on previous study)
Bone marrow aspiration	X ^{5, 6, 12, 13}	End of Cycle 1 ⁵	End of every cycle
Pregnancy test ²	X		
ECHO or gated radionuclide study	X		X
EKG	X		X
Neurologic exam	X		X
Next-generation sequencing (NGS) MRD analysis	With bone marrow evaluation ^{7,13}	With bone marrow evaluation ⁷	With bone marrow evaluation ⁷
Peripheral T cell quantification		X ⁸	X ⁸
Cytokine analysis		X ⁹	X ⁹
Tumor Microenvironment Profiling	X ^{11, 13}		
Flow cytometry with minimal residual disease determination (MRD) ¹⁴		With bone marrow evaluation	With bone marrow evaluation

[^] Studies may be obtained within 72 hours prior to the start of the subsequent cycle.

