12.2.1 Complete Remission (CR)

Attainment of an M1 bone marrow (< 5% blasts) with no evidence of circulating blasts or extramedullary disease and with recovery of peripheral blood counts (ANC $\geq 1000/\text{mm}^3$ and platelet count $\geq 100,000/\text{mm}^3$). Occasionally, rare peripheral blood blasts may be identified during marrow regeneration; however, the marrow must be M1 status by morphology and without Auer rods to be considered CR. Flow cytometry may also be useful to distinguish between leukemia and a regenerating bone marrow. There is no requirement for bone marrow cellularity.

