12.2.3 CR with incomplete blood count recovery (CRI)

Attainment of an M1 bone marrow (< 5% blasts), no evidence of circulating blasts or extramedullary disease and with ANC $< 1000/\text{mm}^3$ or platelet count $< 100,000/\text{mm}^3$ without platelet transfusion independence (defined as no platelet transfusions in 1 week).

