12.2.8 Unevaluable

Aplastic or severely hypocellular marrow with any blast percentage. In this instance, marrow evaluation should be repeated weekly until response determination can be made through at least Day 49.

12.2.9 Bone Marrow Classification:

M1 is < 5% blasts
M2 is 5-25% blasts
M3 is > 25% blasts

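### A patient can enter on flow cytometry alone, but CR is judged by morphology with no comparison to baseline, so an unchanged flow-only entrant can be reported as a remission

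*Combined protocol and SAP*

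**What the plan says.** **Entry.** Section 4.1.4 of the combined protocol and SAP asks for at least "M2 marrow by morphology and/or flow cytometry and one of the following" four disease histories. Section 12.2.9 gives the thresholds, "M1 is < 5% blasts" and "M2 is 5-25% blasts", without naming an assay. Section 4.1.3 adds: "Patients must have histologic verification of malignancy at relapse". Section 4.0 says the criteria are to be read literally and not waived.

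**Remission.** Section 12.2.1 states that "the marrow must be M1 status by morphology and without Auer rods to be considered CR", and treats flow only as a possible help in telling leukemia from a regenerating marrow. CRi in 12.2.3 opens "Attainment of an M1 bone marrow (< 5% blasts), no evidence of circulating blasts or extramedullary disease and with ANC" and continues with low neutrophils, or low platelets without transfusion independence. CRp in 12.2.2 uses the same M1 term. Neither CRp nor CRi says how M1 is measured.

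**Flow schedule.** In the 8.1 table, the row beginning "Flow cytometry with minimal residual disease determination (MRD" has an empty pre-study cell, and the therapy delivery maps list this test at the end of each cycle only. Section 8.5.1, an optional study, describes flow MRD at every marrow time point, and Appendix IX lists a sample before Cycle 1.

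**The concern.** Entry and outcome can be measured with different instruments. A marrow that counts as disease by flow at screening can count as remission by morphology on Day 29 although nothing has happened to it.

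Anti-tumor activity is a secondary aim (1.2.2), and it is to be correlated with disease burden at entry. Flow-only entrants have low morphologic burden by definition, so scoring them as remissions would also push that correlation towards better response at low burden. CR/CRi status defines the groups compared for PK exposure (8.2.1) and immunogenicity (8.3.1), so an unaffected patient could sit in the responder group. The same classification bears on the check after Cycle 2, which asks for PR or better.

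**Working it through.** The plan gives no figure on this point, so the main check sets the definitions side by side for one patient. The blast percentages are assumed for illustration: 7% by flow and 3% by morphology, with no Auer rods, no blasts in the blood and no disease outside the marrow.

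1. **Entry (4.1.4, 12.2.9).** Flow 7% is at or above 5%, so the marrow is M2 by one of the two accepted methods. Section 4.1.8.1 sets no neutrophil minimum and allows platelets from 20,000/mm³ with transfusion, so low counts do not exclude the patient.
2. **Remission at baseline (12.2.1 to 12.2.3).** Morphology 3% is under 5%, so the marrow is M1 by morphology and the CR marrow criterion is met before dosing. Counts then decide the category:
   - neutrophils of at least 1000/mm³ and platelets of at least 100,000/mm³: CR;
   - neutrophils of at least 1000/mm³ and a week without platelet transfusion: CRp, if M1 is read by morphology;
   - neutrophils below 1000/mm³, or platelets below 100,000/mm³ without transfusion independence: CRi, if M1 is read by morphology. No count recovery is needed.
3. **Day 29, marrow unchanged.** There is no 50% rise, so it is not PD (12.2.5). There is no 50% fall, so it is not PR (12.2.4). SD (12.2.6) applies only when no other category does. What remains is the remission category from step 2.
4. **What might stop this.** Only PR requires a fall from baseline, and 12.2.4 leaves PR out of the response calculation, so the reported rate rests on the exposed categories. Response evaluability in 12.2 asks for one cycle, DLT evaluability and one later marrow. It does not ask for disease by morphology at entry.
5. **Other reading of M1.** If M1 and M2 in 12.2.2, 12.2.3 and 12.2.9 carry the either-method meaning of 4.1.4, 7% by flow remains M2 and CRp/CRi fail. The CR route remains, because 12.2.1 names morphology.

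**Size per patient.** Section 11.1 gives up to 18 patients for MTD determination plus up to 6 for PK, so 18 + 6 = 24. As a check, 24/0.9 = 26.7, which rounds up to the plan's 27. A full dose-level cohort is 6. One such patient adds:
- 1/24 = 4.2 percentage points
- 1/18 = 5.6 percentage points
- 1/6 = 16.7 percentage points

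These denominators are planning maxima, not forecasts of the response-evaluable number.

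**Sensitivity to an assumed share.** Let f be the share of patients who enter by flow only, meet the other conditions and stay unchanged. The documents do not give f; 5% to 30% is assumed. Scored rate = f + (1 − f) × true rate. With the adult CR/CRi rate quoted in 2.3.1 (5/27 = 18.5%) as the true rate:
- f = 5%: 0.05 + 0.95 × 0.185 = 22.6%
- f = 10%: 0.10 + 0.90 × 0.185 = 26.7%
- f = 20%: 0.20 + 0.80 × 0.185 = 34.8%
- f = 30%: 0.30 + 0.70 × 0.185 = 43.0%

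**The case against.** Several points on the other side have force.

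- **Relapse confirmation.** Three of the four disease histories involve a relapse, and 12.2.7 requires morphologic confirmation when flow suggests relapse with under 5% blasts. Section 4.1.3 also asks for histology at relapse. This narrows the route. It does not close it: the refractory history involves no relapse, 4.1.4 does not refer to 12.2.7, the histology rule sets no blast threshold, and a confirmed relapse can fall below 5% by morphology before screening.
- **Assay for CRp and CRi.** Morphology is named only in 12.2.1, in the sentence about rare blood blasts during regeneration. A reader might infer that an unchanged flow-only patient plainly meets CRi. The text does not settle that. It depends on reading M1 by morphology, and the missing assay is itself part of the problem.
- **Attainment.** All three definitions speak of attaining M1, which arguably excludes a marrow already M1 at baseline. But a change from M2 by flow to M1 by morphology can be read as attainment, and no rule forbids it.
- **Auer rods.** Their presence rules out CR, and under 12.2.4 such a marrow may be called PR. This removes some patients.
- **Baseline flow.** A reader might infer that no pre-treatment flow MRD is planned. Section 8.5 and Appendix IX do not support that. It is optional rather than absent, and 8.1 and 8.5.1 do not agree.
- **Traceability.** The signed eligibility checklist and pathology report are uploaded, so the qualifying method can probably be recovered. That helps an audit but supplies no scoring rule.
- **Consequence.** Section 11.5 makes response descriptive and exploratory, and it does not enter the MTD/RP2D rules. This stands and limits the importance of the point.

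**Conclusion.** The concern holds in limited form. As written, a patient with 5% or more blasts by flow and under 5% by morphology, with no Auer rods, blood blasts or extramedullary disease, can enter the study, meet the CR marrow criterion at baseline, and be reported as a remission with no change in disease. For CRp and CRi this holds only if M1 is read by morphology.

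Each such patient adds 4.2, 5.6 or 16.7 points with 24, 18 or 6 patients in the denominator. How many there will be is unknown. A reader might take the sensitivity figures as a predicted inflation of the remission rate; the documents do not support that, because they give no share of flow-only entrants. Dose finding is not affected. The exposed results are the descriptive remission rate, its relation to baseline burden, and the CR/CRi groupings for PK and immunogenicity.

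**What to change.** For response reporting, in 12.2:

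- Name the assay for M1 and M2 in 12.2.2, 12.2.3 and 12.2.9.
- State that baseline and response are judged by the same method. Count a patient who qualified only by flow as CR/CRp/CRi only if post-treatment flow is also under 5%. The alternative is to leave flow-only entrants out of the remission rate and report them separately. Choose in advance and apply the choice to all of them, since dropping only those who fail would itself raise the rate.
- Record the qualifying method and the baseline blast percentage by both methods.

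The cost is a short addition to 12.2 and a few data fields. Flow is already required on post-treatment marrows, and the qualifying flow result must be in the patient's record, so the scoring rule needs no new central baseline assay. The documents do not say which laboratory's flow result counts for eligibility, so the two results may come from different laboratories; the report should say so. The reported remission rate may be slightly lower.

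Two matters are for the sponsor to reconcile: 8.1 with 8.5.1 on pre-treatment flow, and how the PR-or-better check after Cycle 2 (5.1, 5.2, 10.1) applies to flow-only entrants. The proposed rule concerns reporting only; no clinical rule is proposed here.

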4.1.8 Organ Function Requirements

4.1.8.1 Adequate Bone Marrow Function Defined as:

- Platelet count $\geq 20,000/\text{mm}^3$ (may receive platelet transfusions).
- Hemoglobin $\geq 8.0 \text{ g/dL}$ at baseline (may receive RBC transfusions)

These patients must not be known to be refractory to red cell or platelet transfusion.

4.1.8.2 Adequate Renal Function Defined as:

- Creatinine clearance or radioisotope GFR $\geq 70\text{ml/min}/1.73 \text{ m}^2$ or
- A serum creatinine based on age/gender as follows:

Age	Maximum Serum Creatinine (mg/dL)	
	Male	Female
1 to < 2 years	0.6	0.6
2 to < 6 years	0.8	0.8
6 to < 10 years	1	1
10 to < 13 years	1.2	1.2
13 to < 16 years	1.5	1.4
≥ 16 years	1.7	1.4

The threshold creatinine values in this Table were derived from the Schwartz formula for estimating GFR (Schwartz et al. J. Peds, 106:522, 1985) utilizing child length and stature data published by the CDC.

4.1.8.3 Adequate Liver Function Defined as:

- Bilirubin (sum of conjugated + unconjugated) $\leq 1.5 \times$ upper limit of normal (ULN) for age regardless of baseline.
- SGPT (ALT) $\leq 3 \times$ ULN. For the purpose of this study, the ULN for SGPT is 45 U/L regardless of baseline.
- SGOT (AST) $\leq 3 \times$ ULN. For the purpose of this study, the ULN for SGPT is 50 U/L regardless of baseline.
- Serum albumin $\geq 2 \text{ g/dL}$.

4.1.8.4 Adequate Cardiac Function Defined As:

- Shortening fraction of $\geq 27\%$ by echocardiogram, or
- Ejection fraction of $\geq 50\%$ by gated radionuclide study.

4.1.8.5 Adequate Neurologic Function Defined as:

- Patients with seizure disorder may be enrolled if on anticonvulsants and well controlled.
- Nervous system disorders (CTCAE v5) resulting from prior therapy must be \leq Grade 2 with the exception of decreased tendon reflex (DTR). Any Grade of DTR is eligible.

4.1.9 Informed Consent: All patients and/or their parents or legally authorized representatives must sign a written informed consent. Assent, when appropriate, will be obtained according to institutional guidelines.

4.1.10 Access: Permanent central access should be established with a central line. A central line that contains 2 lumens is preferred.

